3.2.3 Prior Therapy

- Patients may receive up to a maximum of 5 days of pre-treatment with ATRA prior to administration of protocol therapy.
- Treatment with hydroxyurea, corticosteroids (any route) and intrathecal cytarabine prior to beginning protocol directed therapy is allowed. However, it should be noted that lumbar puncture and intrathecal therapy at initial diagnosis of APL is not recommended due to the possible complications of coagulopathy.

Please see [Section 4.1.3](#) for concomitant therapy restrictions for patients during treatment.

3.2.4 Exclusion Criteria

3.2.4.1 Secondary APL

Patients with secondary APL are excluded. This includes all patients with APL that may have resulted from prior treatment (chemotherapy or radiation).

3.2.4.2 Isolated Myeloid Sarcoma

Patients with isolated myeloid sarcoma (myeloblastoma, chloroma, including leukemia cutis) but without evidence of APL by bone marrow or peripheral blood morphology are excluded.

3.2.4.3 EKG Abnormalities

- Patients with a pre-existing diagnosis of a prolonged QT syndrome (even if QTc is normal at the time of APL diagnosis) are excluded due to the use of arsenic trioxide, which can prolong the QT interval.
- Patients with a baseline QTc of > 450 msec are excluded. Bazett's formula is to be used for measurement of the corrected QT interval: the QT interval (msec) divided by the square root of the RR interval (msec).
- Patients with a history or presence of significant ventricular or atrial tachyarrhythmia are excluded.

- Patients with right bundle branch block plus left anterior hemiblock, bifascicular block are excluded.

3.2.4.4 Renal Dysfunction

Patients with serum creatinine > 3.0 mg/dL and patients on active dialysis for renal dysfunction are excluded.

3.2.4.5 Prior Chemotherapy

Patients who have received treatment with any other cytotoxic chemotherapy prior to beginning protocol therapy (other than allowed in [Section 3.2.3](#)) are excluded.

3.2.4.6 Pregnancy and Breast Feeding

3.2.4.6.1 Female patients who are pregnant are excluded. Treatment under this protocol would expose an unborn child to significant risks. Patients should not be pregnant or plan to become pregnant while on treatment. **There is an extremely high risk of fetal malformation if pregnancy occurs while on ATRA in any amount, even for short periods.**

A pregnancy test prior to enrollment is required for female patients of childbearing potential.

3.2.4.6.2 Lactating females who plan to breastfeed their infants are excluded.

3.2.4.6.3 Sexually active patients of reproductive potential who have not agreed to be abstinent or use 2 forms of effective contraception during treatment through 1 month off therapy are excluded.

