3.2 Patient Eligibility Criteria

Important note: The eligibility criteria listed below are interpreted literally and cannot be waived. All clinical and laboratory data required for determining eligibility of a patient enrolled on this trial must be available in the patient's medical/research record which will serve as the source document for verification at the time of audit.

All clinical and laboratory studies to determine eligibility must be performed within 7 days prior to enrollment unless otherwise indicated. Laboratory values used to assess eligibility must be no older than seven (7) days at the start of therapy. Laboratory tests need not be repeated if therapy starts within seven (7) days of obtaining labs to assess eligibility. If a post-enrollment lab value is outside the limits of eligibility, or laboratory values are > 7 days old, then the following laboratory evaluations must be re-checked within 48 hours prior to initiating therapy: CBC with differential, bilirubin, ALT (SGPT) and serum creatinine. If the recheck is outside the limits of eligibility, the patient may not receive protocol therapy and will be considered off protocol therapy.

For Standard Risk patients see [Section 4.2.2](#) and for High Risk patients see [Section 4.8.2](#) for required studies to be obtained prior to starting protocol therapy.

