4.1 Overview of Treatment Plan

Treatment on this study will consist of an Induction course to achieve an hCR/hCRi, followed by 28 weeks of Consolidation. There is no randomization in this study. Patients will be stratified into risk groups based on WBC at diagnosis. The standard risk group includes patients with $WBC < 10,000/\mu L$, and the high risk group includes patients with $WBC \geq 10,000/\mu L$.

Induction therapy consists of daily arsenic trioxide and twice daily tretinoin for all patients. Patients with high risk APL will also receive 4 doses of idarubicin and prophylaxis dosing of dexamethasone to help prevent differentiation syndrome. All doses of therapy on the protocol should be calculated using actual (not ideal or adjusted) body weight.

Induction will last a minimum of 28 days. Beginning on Day 29 of Induction, patients will have bone marrow testing every 2 weeks as needed to confirm morphologic remission. Induction may last up to a maximum of 70 days. Once in morphologic remission, Consolidation therapy will start a minimum of 14 days after Induction and upon count recovery, whichever occurs later.

Consolidation therapy will be the same for patients with standard risk and high risk APL. Consolidation consists of 28 weeks of therapy including 2 weeks of tretinoin every 4 weeks (7 cycles of tretinoin) and 4 weeks of arsenic trioxide every 8 weeks (4 cycles of arsenic trioxide). After Week 14 of Consolidation (on Day 43 of Cycle 2) there is a bone marrow assessment to determine if patients are in molecular remission (RQ-PCR for PML-RAR α). A clinical sample for RQ-PCR must be sent at that time. Patients not in molecular remission will receive an additional cycle of Consolidation chemotherapy (mitoxantrone, cytarabine and tretinoin) and will again be tested for molecular remission. Those patients in molecular remission will proceed with Cycles 3 and 4 of Consolidation therapy. Those patients not in molecular remission will go off protocol therapy.

A schematic overview of the treatment plan follows:

ATRA= tretinoin

ATO= arsenic trioxide

Induction:

Standard Risk APL (WBC < 10,000/ μ L at diagnosis)

Day: 1.....28

ATRA  (further daily doses if not hCR/hCRi on Day 29 bone marrow)

ATO  (further daily doses if not hCR/hCRi on Day 29 bone marrow)

(Hydroxyurea and dexamethasone will be used to control leukocytosis if WBC rises to > 10,000/ μ L during Induction)

High Risk APL (WBC \geq 10,000/ μ L at diagnosis)

Day: 1.....14.....28

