4.2.2 Required Observations in Induction – Standard Risk APL

All baseline studies must be performed prior to starting protocol therapy unless otherwise indicated below. Obtain other studies during Induction as indicated.

- | |
|---|
| 
 a. History b. Physical Exam with VS: weekly c. Ht, Wt, BSA: Days 1, 29 and 57 d. Performance status e. Pregnancy test: Female patients of childbearing potential require a negative pregnancy test prior to starting treatment; sexually active patients must use an acceptable method of birth control. f. CBC, differential, platelets: daily during Week 1, then at least once weekly g. Urinalysis h. Electrolytes including Ca⁺⁺, Mg⁺⁺, K⁺ and creatinine: daily during Week 1, then at least once weekly i. Uric Acid j. AST, ALT, Total Bilirubin (and Direct Bilirubin if Total Bilirubin is >2 mg/dL): Once weekly k. Cholesterol triglycerides l. PT, PTT, fibrinogen, D-Dimer: daily during Week 1, then on Days 8, 15 and 29 (more frequently if needed for active coagulopathy) m. ECG for QTc monitoring: Weekly n. Echocardiogram or MUGA o. BMA for morphology: At diagnosis and Day 29 and every 2 weeks thereafter as needed until hCR/hCRi p. BMA for flow cytometry, cytogenetics & FISH: At diagnosis q. BMA for clinical RQ-PCR of PML-RARα: At diagnosis. This clinical testing is separate from research samples submitted for the optional MRD study; this mandatory clinical testing is not free of charge (cost is not covered by the study), but the specimen must be sent to one of the approved labs for PML-RARα RQ-PCR testing; a list of approved labs is available on the protocol-specific web page of the COG website. r. FLT3 (optional)*: bone marrow (or peripheral blood if bone marrow is unavailable) at diagnosis. See Section 15.1 for details. s. Research MRD (optional)*: bone marrow and peripheral blood at diagnosis and Day 29 of Induction. See Section 15.2 for details. Results of this research testing will not be returned to sites. This research testing does not take the place of the mandatory RQ-PCR clinical testing that must be done at the time of initial diagnosis (see observation “q” above). t. Coagulopathy (optional)*: peripheral blood at diagnosis (if available), Day 1, Day 8, Day 15 and Day 29 of Induction. See Section 15.3 for details. |
|---|

*Only obtain in patients who have consented to participation in this component of the trial.

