4.3.2 Required Observations in Consolidation Cycle 1 – Standard Risk APL

- a. Physical Exam with VS: Every 4 weeks
- b. Ht, Wt, BSA
- c. CBC, differential, platelets: Weekly while receiving ATO and on Day 29.
- d. Electrolytes including Ca⁺⁺, Mg⁺⁺, K⁺ and Creatinine: Weekly while receiving ATO.
- e. Total bilirubin (and direct bilirubin if total is > 2 mg/dL), AST, ALT: Weekly while receiving ATO and on Day 29.
- f. ECG for QTc monitoring: Weekly while receiving ATO.
- g. Cholesterol, triglycerides
- h. Neurocognitive Testing (optional)*: CogState and BRIEF on Day 1 of Consolidation Cycle 1 (+/- 2 weeks). See [Section 16](#) for details.

*Only obtain in patients who have consented to participation in this component of the trial.

This table only includes evaluations necessary to answer the study aims. Obtain other studies as indicated for good clinical care.

Comments

--

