4.3.3 Consolidation Cycle 1 Treatment Details – Standard Risk APL

Consolidation Cycle 1 lasts 56 days.

Tretinoin (ATRA): PO divided BID

Days: 1 - 14 and 29 - 42

Dose: 12.5 mg/m²/dose, twice daily. The total dose is 25 mg/m²/day divided twice daily.

Administer with food. Refer to [Appendix II](#) for dosing table (includes dose recommendations for very young patients).

Arsenic Trioxide (ATO): IV over 2 hours (may lengthen infusion to 4 hours if active vasomotor symptoms occur)

Days: 1 - 5, 8 - 12, 15 - 19 and 22 - 26

Dose: 0.15 mg/kg/day (no maximum dose)

NOTE: Some patients may require infusion in a clinic setting (i.e. unable to arrange home infusion) and holidays may result in intermittent clinic closure. Therefore it is permissible for patients to miss doses of ATO on those days at the discretion of the treating physician. It is suggested that patients not miss more than 2 doses in a 4 week period (10% of doses). If more than 2 doses are missed in a 4 week period due to holidays, then make-up doses (following Day 26) may be administered at the discretion of the treating physician.

Indications for intrathecal therapy

Intrathecal Triple Therapy (ITT): Only for patients with documented history of CNS bleed or CNS positive disease.

Days: 15 and 43

Dose: Age based dosing as follows:

Age	Triple Intrathecal Therapy (ITT)		
	Methotrexate	Hydrocortisone	Cytarabine
1 - 1.99 years	8 mg	15 mg	30 mg
2 - 2.99 years	10 mg	25 mg	50 mg
≥ 3 years	12 mg	35 mg	70 mg

Proceed to Consolidation Cycle 2 on Day 57 or when blood counts recover (ANC ≥ 1,000/μL and platelet count ≥ 100,000/μL), whichever occurs later. See [Section 4.4](#) for details.

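### Pregnancy testing is required only at baseline, although tretinoin is restarted seven times in Consolidation, the last time at least 30 weeks after Induction Day 1

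*Combined protocol and SAP*

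**What the plan says.** Section 3.2.4.6 excludes pregnant patients and gives the reason in bold: "There is an extremely high risk of fetal malformation if pregnancy occurs while on ATRA in any amount, even for short periods". The testing rule that follows is "A pregnancy test prior to enrollment is required for female patients of childbearing potential".

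The Induction observation lists repeat the requirement. Item (e) of section 4.2.2 (standard risk) reads "Female patients of childbearing potential require a negative pregnancy test prior to starting treatment", and item (e) of section 4.8.2 (high risk) has the same words. Both Induction delivery maps schedule that item on Day 1 only.

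Section 3.2 adds that "Laboratory values used to assess eligibility must be no older than seven (7) days at the start of therapy". A single test in the baseline window can therefore satisfy both the enrolment rule and the pre-treatment rule.

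After Induction, section 4.1 plans 28 weeks of Consolidation with seven blocks of tretinoin. For Cycles 1 to 3 the tretinoin schedule is "Days: 1 - 14 and 29 - 42"; in Cycle 4 and in MRD Positive Consolidation it is Days 1 to 14. The protocol's other pregnancy provisions are:

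- abstinence or two contraceptive methods until one month off therapy, for sexually active patients (3.2.4.6.3);
- an acceptable birth-control method for sexually active patients (4.2.2(e) and 4.8.2(e));
- removal from protocol therapy for pregnancy (8.1(k)).

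**The concern.** The protocol regards tretinoin exposure in pregnancy as dangerous at any dose and for any duration. It therefore requires a negative test before the first exposure. The same reasoning applies each time the drug is stopped and started again, and the breaks between blocks are natural points at which to check. The schedule does not use them.

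A patient who becomes pregnant after baseline could be given tretinoin again with no required test in between. Whether the pregnancy is found first would depend on her reporting it, on a clinical examination raising suspicion, or on the site choosing to test. The stake is avoidable fetal exposure. Event-free survival, type I error, power and sample size are not touched.

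**Working it through.** **Step 1. Is a test required anywhere after baseline?** Every required-observation list was read for a pregnancy test.

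| Phase | Standard risk | High risk | Pregnancy test listed? |
|---|---|---|---|
| Induction | 4.2.2 | 4.8.2 | Yes, baseline only |
| Consolidation Cycle 1 | 4.3.2 | 4.9.2 | No |
| Consolidation Cycle 2 | 4.4.2 | 4.10.2 | No |
| MRD Positive Consolidation | 4.5.2 | 4.11.2 | No |
| Consolidation Cycle 3 | 4.6.2 | 4.12.2 | No |
| Consolidation Cycle 4 | 4.7.2 | 4.13.2 | No |
| End of therapy and follow-up | 7.2 | 7.2 | No |

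**Step 2. Reproduce the plan's own figures.** Cycles 1 to 3 last 56 days each and Cycle 4 lasts 28 days.

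- Consolidation length: 56 + 56 + 56 + 28 = 196 days = 28 weeks, as section 4.1 states.
- Tretinoin blocks: 2 + 2 + 2 + 1 = 7, also as stated. MRD Positive Consolidation adds one, making 8.

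**Step 3. Date the restarts.** Induction lasts 28 to 70 days, and "Consolidation therapy will start a minimum of 14 days after Induction". Counted from Induction Day 1:

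- Cycle 1 Day 1 = 28 + 14 = 42 days = week 6.
- Restarts then follow every 4 weeks: weeks 6, 10, 14, 18, 22, 26 and 30.
- Last restart (Cycle 4 Day 1) = 28 + 14 + 3 × 56 = 210 days = week 30.
- End of therapy = week 30 + 4 = week 34.

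A 70-day Induction adds 42 days (6 weeks). The MRD Positive cycle adds 28 days (4 weeks).

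| Induction | MRD Positive cycle | Restarts | Last restart | End of therapy |
|---|---|---|---|---|
| 28 days | No | 7 | week 30 | week 34 |
| 28 days | Yes | 8 | week 34 | week 38 |
| 70 days | No | 7 | week 36 | week 40 |
| 70 days | Yes | 8 | week 40 | week 44 |

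These are minimum times, because each cycle also waits for blood counts to recover. If the baseline test was already 7 days old at the start of therapy, add one week to the interval since the last required test: 30 to 31 weeks on the shortest schedule.

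**Step 4. With a test before every block.** There would be 4 Day 1 tests and 3 Day 29 tests, 7 in all, or 8 with the MRD Positive cycle. The longest scheduled gap between required tests would be from baseline to Cycle 1: 6 to 7 weeks after a 28-day Induction and 12 to 13 weeks after a 70-day one. Later gaps would be 4 weeks at minimum.

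**Step 5. How many patients?** Section 9.5 expects 73 + 21 = 94 females among 158 enrolments. Eligibility runs from 12 months to under 22 years of age, and the share of childbearing potential is not given, so no total can be stated.

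**The case against.** The strongest case against has four parts.

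*The tables are not the whole plan.* Each list says that it covers only what the study aims need and leaves other tests to good clinical care. Section 6.0 sends readers to the consent document for toxicities and to separate drug monographs for other drug information. Neither was available for this review, and either might advise repeat testing. That limit stands. It does not change what the protocol's own lists require, and the Induction lists carry the same disclaimer yet still include a pregnancy test. It is fair to reply that the Induction test serves an eligibility criterion, but the reason for that criterion, fetal harm, continues throughout tretinoin treatment.

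*Other safeguards exist.* Contraception or abstinence is the main preventive control, pregnancy ends protocol therapy, and physical examinations are scheduled about every four weeks. These lower the risk. However, the two-method rule is an entry criterion for patients who are sexually active, and contraception can fail. Appendix IV itself lists some oral contraceptives among drugs that may interact with tretinoin. Removal for pregnancy works only once the pregnancy is known, and an examination is not a test.

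*The remedy is incomplete.* A test at the start of a block cannot detect conception during that block. The proposal also adds nothing during a long Induction or after toxicity holds. This is correct: testing narrows the gap and does not close it.

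*The frequency is a judgement.* The documents do not dictate seven tests. True, but testing before each block follows directly from how the drug is scheduled.

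**Conclusion.** The concern holds. For each patient of childbearing potential who completes therapy, the protocol schedules seven tretinoin restarts (eight with MRD Positive Consolidation) and no required pregnancy test after baseline. The last restart falls between week 30 and week 40 from Induction Day 1, before any count-recovery delay.

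The conclusion rests on the protocol's required-observation lists and delivery maps. It assumes nothing about what sites do on their own initiative or what the consent document and drug monographs say. The expected number of exposed pregnancies is unknown, and none is claimed. The change is worth making because the protocol itself describes the harm as severe at any exposure, and the remedy is simple. It has no bearing on the validity of the efficacy results.

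**What to change.** In both risk groups, add a pregnancy test for female patients of childbearing potential to the required observations:

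- on Day 1 of Consolidation Cycles 1, 2, 3 and 4;
- on Day 29 of Cycles 1, 2 and 3;
- on Day 1 of MRD Positive Consolidation.

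Require the result to be reviewed before tretinoin is restarted. Have childbearing potential re-assessed each time, since a girl may reach it during roughly eight months of treatment. As an editorial matter, items 4.2.2(e) and 4.8.2(e) should cross-refer to the abstinence or two-method rule in 3.2.4.6.3.

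The cost is seven inexpensive tests per patient concerned (eight with the MRD Positive cycle) and an amendment to the observation tables and delivery maps. No visits are added. The Cycle 1 list already has "CBC, differential, platelets: Weekly while receiving ATO and on Day 29", Cycles 2 and 3 follow the same pattern, and bloods are also listed on Day 1 of Cycle 4 and of MRD Positive Consolidation. A pending result might hold up a restart briefly; section 4.0 already accepts unavoidable departures of up to 72 hours.

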3.2.5 Regulatory Requirements

3.2.5.1 All patients and/or their parents or legal guardians must sign a written informed consent.

3.2.5.2 All institutional, FDA, and NCI requirements for human studies must be met.

3.3 **Definitions**

3.3.1 Initial CBC

The first CBC from the COG treating institution.

3.3.2 Standard Risk

Patients with a WBC < 10,000/ μ L on the initial CBC at diagnosis are defined as standard risk.

3.3.3 High Risk

Patients with a WBC $\geq 10,000/\mu\text{L}$ on the initial CBC at diagnosis are defined as high risk.

3.3.4 CNS Disease and CNS Bleed

3.3.4.1 CNS disease is defined as:

- Any number of blasts on a cytospin prep in an atraumatic (< 100 RBCs) lumbar puncture.*
- Blasts in a traumatic tap in which the WBC/RBC ratio in the CSF is twice that in the peripheral blood.*
- Clinical signs of CNS leukemia (such as facial nerve palsy or hypothalamic syndrome). Patients with retinal hemorrhage alone do not have CNS leukemia. Patients with documented CNS bleed and with neurologic symptoms that are fully attributable to the CNS bleed do not have CNS leukemia unless they meet one of the other criteria in this section (CSF or chloroma) but these patients do meet criteria for “CNS Bleed”. See Section [3.3.4.2](#) below.
- Radiographic evidence of an intracranial, intradural mass consistent with a chloroma.

*NOTE: For patients who are diagnosed with CNS disease based on blasts in the CSF, we strongly recommend that you contact the COG APL investigator [name] to discuss central review of the CSF slides. [name] can be contacted at [contact] and he will provide shipping information upon contact.

3.3.4.2 CNS Bleed is defined as:

- Any radiographic evidence of hemorrhage into the brain parenchyma, spinal cord or subarachnoid, subdural or epidural spaces.
- Retinal hemorrhage alone is not a CNS bleed.

3.3.4.3 Method of Evaluating Initial Traumatic Lumbar Punctures:

If the patient has leukemic cells in the peripheral blood and the lumbar puncture is traumatic and contains blasts, the following algorithm should be used to diagnose CNS disease:

$$\frac{\text{CSF WBC}}{\text{CSF RBC}} > 2X \frac{\text{Blood WBC}}{\text{Blood RBC}}$$

A patient with CSF blasts, whose CSF WBC/RBC is 2X greater than the blood WBC/RBC ratio, has CNS disease at diagnosis. Example: CSF WBC = 60/ μL ; CSF RBC = 1,500/ μL ; blood WBC = 46,000/ μL ; blood RBC = 3 X 10⁶/ μL :

$$\frac{60}{1,500} = 0.04 > 2X \frac{46,000}{3 \times 10^6} = 0.015$$

4.0 TREATMENT PLAN

Timing of protocol therapy administration, response assessment studies, and surgical interventions are based on schedules derived from the experimental design or on established standards of care. Minor unavoidable departures (up to 72 hours) from protocol directed therapy and/or disease evaluations (and up to 1 week for surgery) for valid clinical, patient and family logistical, or facility, procedure and/or anesthesia scheduling issues are acceptable (except where explicitly prohibited within the protocol).

4.1 Overview of Treatment Plan

Treatment on this study will consist of an Induction course to achieve an hCR/hCRi, followed by 28 weeks of Consolidation. There is no randomization in this study. Patients will be stratified into risk groups based on WBC at diagnosis. The standard risk group includes patients with $WBC < 10,000/\mu L$, and the high risk group includes patients with $WBC \geq 10,000/\mu L$.

Induction therapy consists of daily arsenic trioxide and twice daily tretinoin for all patients. Patients with high risk APL will also receive 4 doses of idarubicin and prophylaxis dosing of dexamethasone to help prevent differentiation syndrome. All doses of therapy on the protocol should be calculated using actual (not ideal or adjusted) body weight.

Induction will last a minimum of 28 days. Beginning on Day 29 of Induction, patients will have bone marrow testing every 2 weeks as needed to confirm morphologic remission. Induction may last up to a maximum of 70 days. Once in morphologic remission, Consolidation therapy will start a minimum of 14 days after Induction and upon count recovery, whichever occurs later.

Consolidation therapy will be the same for patients with standard risk and high risk APL. Consolidation consists of 28 weeks of therapy including 2 weeks of tretinoin every 4 weeks (7 cycles of tretinoin) and 4 weeks of arsenic trioxide every 8 weeks (4 cycles of arsenic trioxide). After Week 14 of Consolidation (on Day 43 of Cycle 2) there is a bone marrow assessment to determine if patients are in molecular remission (RQ-PCR for PML-RAR α). A clinical sample for RQ-PCR must be sent at that time. Patients not in molecular remission will receive an additional cycle of Consolidation chemotherapy (mitoxantrone, cytarabine and tretinoin) and will again be tested for molecular remission. Those patients in molecular remission will proceed with Cycles 3 and 4 of Consolidation therapy. Those patients not in molecular remission will go off protocol therapy.

A schematic overview of the treatment plan follows:

ATRA= tretinoin

ATO= arsenic trioxide

Induction:

Standard Risk APL (WBC < 10,000/ μ L at diagnosis)

Day: 1.....28

ATRA  (further daily doses if not hCR/hCRi on Day 29 bone marrow)

ATO  (further daily doses if not hCR/hCRi on Day 29 bone marrow)

(Hydroxyurea and dexamethasone will be used to control leukocytosis if WBC rises to > 10,000/ μ L during Induction)

High Risk APL (WBC \geq 10,000/ μ L at diagnosis)

Day: 1.....14.....28

ATRA  (further daily doses if not hCR/hCRi on Day 29 bone marrow)

ATO  (further daily doses if not hCR/hCRi on Day 29 bone marrow)

[figure not shown]
Dex 

Ida **X X X X**

(Ida= Idarubicin given on Days 1, 3, 5, 7)

Consolidation:

Standard Risk and High Risk APL

(*Only if Week 14 RQ-PCR of PML-RAR α positive, repeat testing in 1-2 weeks. If repeat test is confirmed positive continue to MRD Positive Consolidation)

See the Chemotherapy Administration Guidelines (CAG) for children on the COG website at:

https://cogmembers.org/_files/disc/Pharmacy/ChemoAdminGuidelines.pdf for special precautions and suggestions for patient monitoring. As applicable, also see the CAG for suggestions on hydration, or hydrate according to institutional guidelines.

